Data Management. The project's data manager will conduct all data management and analysis activities under the supervision of Drs. [name] and [name]. Research staff will use double entry procedures and reconcile discrepancies. Data cleaning will be conducted throughout data collection to ensure a quality final dataset for analysis. Statistical Analysis System (SAS) will be used to examine and prepare data for the analysis.

General analytic approach. Hypotheses will be planned a priori, and will be limited to the examination of a limited number of outcomes. We will utilize an "intent-to-treat" approach. All analyses will use two-sided tests because it is possible that the APM participants might have worse outcomes compared to CBA participants. Analyses will begin with descriptive data analyses to determine distributions of key variables, to collapse categories, if necessary, and to review data for outliers and clear anomalies. Tests for linearity, independence, missingness, and distributional assumptions will also be performed. Normalizing transformations of the dependent variables will be utilized, if necessary. We will validate the randomization scheme by comparing the initial groups on key variables that could be associated with the outcomes. Where we identify significant differences between groups, we will adjust for these variables, as well as other addictions treatment received if it was not initiated by referral from the APM or CBA clinician (and thus a potential mediator of effect). Prior to fitting any analytic models, a graphical exploration of the outcome variables will be conducted to select the appropriate models based on variable distributions.

Missing data. Every effort will be made to minimize missing data. Where we have missing covariates that are necessary for analysis, we will perform multiple imputation of missing data and combine the results from 5 imputations based on Rubin's method to produce an estimate and the corresponding confidence interval accounting for missing data uncertainty.⁸⁸ For follow-up attrition, the proposed mixed-effects regression model will allow the use of data from all participants (not just those with complete follow-up) and provide unbiased

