parameter estimates that account for missing data under the missing-at-random assumption.⁸⁹ We will look for non-random attrition, and if we find, for example, attrition rates to depend on a baseline covariate, we will include this covariate in the model. If we find attrition to depend on treatment use or ideation at prior assessments, we will utilize an appropriate pattern mixture model or multiply impute data based on an appropriate pattern mixture model assumptions based on the observed missing data pattern.⁸⁸

Aim 1: Determine the efficacy of the ED APM intervention compared to BA on TLFB drinking frequency reports at 3-, 6-, and 12-months post-baseline. **Hypothesis:** Veterans with hazardous drinking who are randomly assigned to APM will have significantly greater reductions in total TLFB drinking frequency reports, compared to those assigned to CBA.

Data Analysis for Aim 1: The primary purpose of Aim 1 is to examine the impact of the intervention on frequency of drinking per TLFB interview. This outcome will likely follow the assumptions required for linear regression model, but we will adjust the model type as needed. Assuming this is the case; we will use a linear mixed-effects model and estimate the treatment effect as the difference in the time-averaged TLFB frequencies over the year of follow-up. Because reduction in problem alcohol use is of primary interest, the analysis will model change-scores from baseline in the response variable as dependent variable, and the independent variables will include the baseline values of the response variable, time in months since randomization, and the treatment group indicator. The parameter estimate of the treatment group indicator will estimate the time-averaged treatment effect. *In a second model, we will include an interaction of time by treatment group indicator to formally test the possibility that the effect varies over time. Models will include a random effect for which specific peer/clinician a participant was assigned.*

Aim 2: Determine the impact of the APM intervention on linkage to primary and specialty alcohol treatment services care, mental health symptoms and functioning at 3-, 6-, and 12-months post-baseline, compared to BA. **Hypothesis:** Veterans with hazardous drinking who are randomly assigned to APM will be significantly more likely to engage in primary, specialty care, and other VHA supportive services and to have improvements in mental health symptoms and functioning.

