Data Analysis for Aim 2: The focus of Aim 2 is to study intervention effects on secondary outcome of frequency of primary care and mental health specialty care visits (as two separate outcomes) from the TSR, calculated as an average number of visits per month during each follow-up period. Similar to Aim 1, analyses will generally use a mixed effect model framework. As described above, initial analyses will examine the distribution of outcome measures over follow-up in order to select an appropriate model (e.g. Poisson regression or a related method for counts of visits). Our analysis strategy will parallel Aim 1 in terms of the independent variables, *random effect for peer/brief advice, focus on time-average treatment effects, and additional modeling of interactions of group and time.*

Secondary Aim will determine the mediators (e.g., motivation to change, self-efficacy, coping, social support) of the effect of the intervention and linkage on subsequent alcohol use and alcohol-related consequences. **Hypothesis:** The effect of randomization to APM compared to BA on the primary outcomes (i.e., alcohol consumption and consequences) will be mediated by differences between groups in motivation to change, self-efficacy, and perceived helpfulness of peer support.

Data Analysis for Secondary Aim: *In order to establish temporal ordering, we will examine whether level of the hypothesized mediators at 3 and 6 months post-baseline mediates the effect of random assignment on 6- and 12-month measures of the three primary outcomes of alcohol use behaviors.^{90,91} We will first determine the whether study condition is associated with the hypothesized mediators over the first six months of follow-up and check for a direct effect of the mediators at 3 and 6 months on alcohol use as measured at 6- and 12-months follow-up. We will estimate the indirect effect of the intervention on alcohol use through the mediators and conduct significance testing of this effect using macros created by Preacher and Hayes.⁹²*

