Data Analysis for Exploratory Aim: Interviews will be audiotaped and transcribed verbatim for content. We will conduct analyses. We will use a rapid data analysis process, a technique used when there is a need for targeted, actionable information.⁹³ The research team will read early transcripts independently, and, in an iterative process, meet to develop and refine the coding scheme and code definitions, including developing new codes from the data based on ongoing data analysis. We will document code definitions, data interpretation, and analytic decisions in memos. Once the research team has agreed on codes and code definitions, Drs. [name] and [name], and the research supervisor, will independently review and code transcripts, meeting regularly to compare coding results, and resolving discrepancies through a consensus process. If coding definitions are refined during this process, the coders will recode transcripts already coded. Once data are coded, we will use QSR NVivo 10 software to organize the data. The study team will meet regularly to discuss code summaries and memos, developing findings with a focus on barriers and facilitators to implementation and potential testable implementation strategies. Members of the study team have used similar methods in a study of the acceptability of peer support interventions in Michigan NG soldiers.^{94,95}

Power and Sample Size Calculations

Of 450 participants randomized, we expect that at least 80% of participants will be retained (n=360). We conservatively have estimated power without accounting for methods that will allow inclusion of participants with partial follow-up data because this benefit will be off-set to an unknown degree by the additional parameters estimated in a mixed effects model. All power analyses used G*Power 3.1.9 software and a two-sided $\alpha = .05$. We calculated power based on several potential outcome measure distributions. If a linear model is appropriate, which we expect to be the case for the primary outcome of total AUDIT scores, we achieve 80% power to detect an effect size (Cohen's d) of 0.30. This is a relatively modest and reasonable effect size for studies of SBIRT models of alcohol brief interventions. For an outcome with a count distribution and assuming a mean level in controls of 1 (e.g., an average of 1 alcohol-related treatment visit in a follow-up period), we achieve 80% power to detect an incidence rate ratio of 0.75 or 1.34 under a Poisson framework.

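### Five imputations is too few for a reproducible p-value wherever imputation is used; raising the number costs only computing time, but the default Aim 1 analysis is largely untouched

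*Combined protocol and SAP*

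**What the plan says.** All of this is in the combined protocol and SAP.

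- **Covariates.** Under Missing data: "Where we have missing covariates that are necessary for analysis, we will perform multiple imputation of missing data". The analyst is to "combine the results from 5 imputations" by Rubin's method. This is the only number of imputations in the document.
- **Missing outcomes, default.** The same section treats dropout separately: "For follow-up attrition, the proposed mixed-effects regression model will allow the use of data from all participants". This rests on missing at random and involves no imputation.
- **Missing outcomes, conditional route.** "If we find attrition to depend on treatment use or ideation at prior assessments", the analyst may use a pattern-mixture model "or multiply impute data based on an appropriate pattern mixture model assumptions". No number of imputations is given.
- **Which covariates.** Under General analytic approach, the models adjust for baseline variables on which the groups differ, and for addiction treatment that did not come from the study's own referral. The second is a post-baseline variable.
- **Mediators.** Data Analysis for Secondary Aim states: "we will examine whether level of the hypothesized mediators at 3 and 6 months post-baseline mediates" the effect of assignment on later drinking. It does not say what happens when a mediator is missing.
- **Retention.** Power and Sample Size Calculations: "we expect that at least 80% of participants will be retained", that is 360 of 450.

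The document fixes no random seed and plans no report of Monte Carlo error.

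**The concern.** With few imputations, the pooled estimate and its standard error carry simulation noise. The between-imputation variance, which is meant to carry the uncertainty due to missing data, is then estimated from only five values. If a meaningful share of the information is imputed, the same data and the same model give different p-values under different seeds, and a result near 0.05 can be significant in one run and not in the next.

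The covariate rule can reach variables with real missingness. Treatment outside the study's referral is measured partly by self-report at the follow-up visits, so it is exposed to dropout. The covariate rule is also the only stated rule that could be applied to missing 3- and 6-month mediators. If the conditional outcome imputation were used, 5 is the only figure in the plan that an analyst could carry over.

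**Working it through.** **Inputs.** From the plan: m = 5 imputations; two-sided alpha 0.05; 80% power for d = 0.30; 225 randomized per arm; at least 80% retained, so 180 per arm at the floor. Not in the plan: the fraction of missing information (FMI), written λ below. It is assumed to lie between 0.05 and 0.30. The value 0.20 matches the largest expected dropout, and 0.05 is closer to sparsely missing baseline covariates. FMI is not the same as the proportion missing: good predictors lower it, and joint loss of a mediator and a later outcome could raise it.

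**Step 1: the plan's own figure.** With 180 per arm and d = 0.30, 0.30 × √(180/2) = 2.846, and 2.846 − 1.960 = 0.886, so power is 81.2% (81.0% with the noncentral t). The stated 80% is reproduced.

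**Step 2: cost of a finite m.** Relative efficiency is 1/(1 + λ/m). Standard error inflation is √(1 + λ/m) − 1. Seed-to-seed error, in units of the standard error, is √(λ/m). At λ = 0.20 and m = 5: 1/1.04 = 96.2%; √1.04 − 1 = 2.0%; √0.04 = 0.20.

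| λ | SE inflation, m = 5 | Seed error, m = 5 | Seed error, m = 20 | Seed error, m = 50 |
|---|---|---|---|---|
| 0.05 | 0.5% | 0.100 | 0.050 | 0.032 |
| 0.10 | 1.0% | 0.141 | 0.071 | 0.045 |
| 0.20 | 2.0% | 0.200 | 0.100 | 0.063 |
| 0.30 | 3.0% | 0.245 | 0.122 | 0.077 |

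At λ = 0.20, relative efficiency is 99.0% with m = 20 and 99.6% with m = 50. The coefficient of variation of the between-imputation variance is √(2/(m − 1)): √(2/4) = 0.71 with m = 5 and √(2/49) = 0.20 with m = 50.

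**Step 3: what this does to a borderline p-value.** Rubin's rules were simulated with small-sample degrees of freedom (357 for complete data), holding the data fixed and changing the seed. The starting point is a result that would have p = 0.040 with unlimited imputations.

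| λ | m | Central 95% range of p over seeds | Share of seeds with p < 0.05 |
|---|---|---|---|
| 0.05 | 5 | 0.024 to 0.068 | 78% |
| 0.20 | 5 | 0.012 to 0.133 | 56% |
| 0.20 | 20 | 0.023 to 0.071 | 75% |
| 0.20 | 50 | 0.028 to 0.057 | 88% |

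**Step 4: over all trials, not only borderline ones.** Where power would be 80% with unlimited imputations, m = 5 gives 79.5%, 78.9%, 77.0% and 74.7% at λ = 0.05, 0.10, 0.20 and 0.30. At λ = 0.20, m = 50 gives 79.8%. Two seeds reach opposite verdicts at 0.05 in 9.4% of trials with m = 5, 3.9% with m = 20 and 2.4% with m = 50.

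These figures are for the test of a single coefficient. They have not been shown to carry over exactly to the indirect-effect test in the mediation analysis.

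**The case against.** The strongest objection is to scope. A reader might infer that five imputations govern all missing data, so that mediators and outcomes missing for up to about 20% will be filled in five times and the primary p-value will turn on a seed. The documents do not support that:

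- The number is attached to covariates. The next sentence handles dropout in the mixed model without imputation.
- The named predictors in the Aim 1 model are the baseline value, time and arm.
- The outcome-imputation route opens only if attrition is found to depend on earlier treatment use or ideation. Even then it is one of two options, and no number is stated for it.
- The mediators are not called covariates, and nothing says they will be imputed.
- The 80% retention figure is a floor.
- VHA records can fill part of any gap in the treatment covariate.

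All of this stands.

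A reader might also infer a serious loss of precision. That does not stand either: 2% in the standard error at λ = 0.20 and 0.5% at λ = 0.05 are small.

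What survives is narrower. Wherever imputation is used, five is low, nothing in the plan limits or reports the resulting noise, and a larger number has no statistical cost. The plan's silence on missing mediators is itself a reason to clarify.

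**Conclusion.** This is a minor point, and it holds in conditional form. The plan fixes five imputations for missing covariates. The default Aim 1 test depends on a seed only if a covariate is imputed, for example addiction treatment from outside the study's referral, or if the pattern-mixture imputation is used. The mediation results are affected only if missing mediators are imputed under the same rule.

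Under the assumed λ of 0.05 to 0.30, the standard error is inflated by about 0.5% to 3% and the seed-to-seed error is 0.10 to 0.24 standard errors. That is enough to move a borderline result across 0.05, and it matters little for a clear result. The weakness is in reproducibility; the loss of precision is secondary. The conclusion that a larger number is better does not depend on the assumed λ. Its size does.

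**What to change.** 1. Under Missing data, replace the five imputations with a clearly larger number, for example 50. Twenty already gives 99.0% efficiency at λ = 0.20, but 50 cuts the seed-to-seed error further, from 0.10 to 0.06 standard errors.
2. Add a sentence applying that number to any imputation under the conditional pattern-mixture route. That text now gives no number, so an addition is needed there.
3. In Data Analysis for Secondary Aim, say how missing mediators are handled and, if they are imputed, that the same number applies.
4. Fix the seed in the analysis program before the outcome analysis is run, and report the Monte Carlo error of the main estimates. A fixed seed alone only makes one arbitrary answer repeatable; the larger number removes most of the arbitrariness.

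The cost is a few lines of text and some computing time. Participants, sample size and estimand are unaffected.

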ED Staffing / Subject Accrual. Because it is not possible to staff the project continuously (168 hours/week), this study will use the following sampling frame that has been used successfully in our previous ED research to ensure obtaining a representative sample of Veterans presenting to the AAVA ED. Project staff in the ED will recruit patients for the study 5 days per week between the hours of 10AM to 6PM. The majority of the recruitment time will be spent in the ED between 10AM and 6PM because 65-70% of patients enter the ED during those hours. In addition, another three days/week will include a weighted sampling of recruiting between either 7AM-3PM or 3PM-11PM time period. Thus, a total of 8 shifts (8 hours each) will be staffed each week to recruit, consent, screen patients, conduct baseline assessments, and deliver brief advice. Based on our previous ED studies where we have used similar staffing schedules we expect to accrue the following numbers: 30 months of screening x ~130 patients/month approached = 3,900; it is expected that 80% (n=3,120) will agree to participate and will be screened. We conservatively expect that 15% of the screened patients will have a positive screen and will be randomized (450 randomized; 225 per group). Randomization Procedures. Stratified random assignment to conditions will be by sex and presence of an AUD (yes/no) defined as a score of 14 for men and 10 for women on the AUDIT. Randomization by sex will be used because men and women generally differ in their rates and nature of alcohol use, problems, and outcomes. Random assignment will also be stratified based on meeting criteria for past year AUD (yes/no) because of potential differences in problem severity and potential intervention response. Randomization will proceed in blocks of 10 within study cells, in order to equalize randomization over time. Follow-up staff will be blind to condition. Participants in both conditions will receive written information regarding alcohol and VHA resources and be re-contacted to complete 3-, 6-, and 12-months follow-ups.

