We expect that 15% of the screened patients will have a positive screen and will be randomized, yielding 225 per group (total=450). Based on data from the study site, we anticipate the gender composition of the sample to be approximately 7.5% female and 92.5% male; we expect the following racial composition of the sample: approximately 20% African American, 75% Caucasian, and 5% other (i.e., Asian, American Indian, Native Hawaiian or Other Pacific Islander). We also expect that 1-2% of adults will identify as Hispanic ethnicity.

Inclusion criteria for screening. 1) adult Veterans age 18 years of age or older presenting for care in the VAAAHS ED; 2) medically stable and able to provide informed consent.

Inclusion criteria for the RCT. Individuals will be eligible to participate in the RCT if they: (1) have an AUDIT-C score of 4 or more for men and 3 or more for women in the prior 3 months, indicating that they meet criteria for hazardous use (NIAAA 2005; World Health Organization); 2) a telephone and/or the ability to provide information about individuals who can help contact the participant. Importantly, the study will include those with more severe problems to address the problems and needs of Veterans who can most benefit from linkage to primary and secondary care. The more severe users will receive content that actively encourages treatment initiation.

Exclusion criteria for screening. (1) patients who do not understand English; (2) prisoners; (3) current or recent substance use treatment in past 3 months; (4) patients currently in or having received peer services in the past 3-months per medical record; (5) pregnant women; (6) patients deemed unable to provide informed consent as stated above; and (7) profound psychotic symptoms and/or cognitive deficits that would prevent patients from understanding the content of the intervention and/or assessments.

It has been our experience that some patients are unable to provide informed consent on entry to the ED (e.g. psychotic symptoms; acute intoxication) but that their status will improve sufficiently prior to ED discharge to make them eligible to be approached by research staff. Participants may be excluded at the discretion of the Principal Investigator based on participant or study staff best interest (e.g., if participant should become physically or verbally aggressive towards study staff, or if the study staff know a patient or their family

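### Sex and AUD stratify the randomisation but are missing from the Aim 1 and Aim 2 models, and a baseline significance rule chooses the covariates instead

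*Combined protocol and SAP*

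**What the plan says.** Under Randomization Procedures the plan states "Stratified random assignment to conditions will be by sex and presence of an AUD (yes/no", with AUD defined by an AUDIT score of 14 for men and 10 for women, and "Randomization will proceed in blocks of 10 within study cells". The reason given for sex is prognostic: "Randomization by sex will be used because men and women generally differ in their rates and nature of alcohol use, problems, and outcomes". The reason given for AUD is part prognostic (problem severity) and part possible difference in response to the intervention.

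Data Analysis for Aim 1 specifies a linear mixed model of change from baseline in which "the independent variables will include the baseline values of the response variable, time in months since randomization, and the treatment group indicator". It adds a random effect for the peer or clinician. For Aim 2, "Our analysis strategy will parallel Aim 1 in terms of the independent variables".

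General analytic approach describes a check of the randomisation by "comparing the initial groups on key variables that could be associated with the outcomes", followed by: "Where we identify significant differences between groups, we will adjust for these variables". The variables to be compared and the significance level are not given. Later in the analysis section, gender is a model variable only in the analysis of session attendance, and baseline severity appears as a potential moderator and as a predictor of attendance.

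**The concern.** The two factors that the plan judged important enough to constrain the allocation are not in the models that compare the arms. When a prognostic factor is balanced by design but left out of the model, its variance stays in the residual term although it no longer contributes to the difference between arms. The reported standard error is then larger than the true one, intervals are too wide and the test is conservative.

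The fallback rule does not repair this. A significance test of baseline differences in a randomised trial tests a null hypothesis already known to be true. It picks up chance imbalance and does not measure how strongly a variable predicts drinking. Blocking within strata keeps sex and AUD nearly equal between arms, so the rule will almost never select them, while it may admit other variables by chance. The covariate set of the primary model is therefore not fixed before the data are seen.

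**Working it through.** **Inputs from the documents.** 450 randomised 1:1; 80% retained, so 360 analysed, 180 per arm; two-sided alpha 0.05; d = 0.30; stated power 80% (Power and Sample Size Calculations). Sex mix "approximately 7.5% female and 92.5% male" (Human Subjects Involvement and Characteristics). The power section attaches d = 0.30 to total AUDIT scores although the TLFB is the named primary outcome. Because d is standardised, this does not affect the arithmetic here.

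**Assumed input.** R² is the share of the residual variance, after baseline drinking, that sex and AUD explain together. The documents give no value. I take 0.02 to 0.05 as the working range, with 0.01 and 0.10 as outer cases.

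**Step 1: the plan's own figure.** Two-sample t test with noncentrality 0.30 × √(180/2) = 2.846, 358 degrees of freedom and critical value 1.967. Power is 81.0%, which agrees with the stated 80%.

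**Step 2: power with and without the strata.**
- Included: the effect size becomes 0.30/√(1 − R²).
- Omitted under stratified randomisation: the estimate is already less variable, but the model does not credit it. Power = 1 − Φ[(1.967 − 2.846)/√(1 − R²)].
- True size when omitted = 2 × [1 − Φ(1.96/√(1 − R²))].
- Overstatement of the standard error = 1/√(1 − R²) − 1.

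| R² (assumed) | Power, included | Power, omitted | Loss (points) | True size, omitted | SE overstated by |
|---|---|---|---|---|---|
| 0.01 | 81.4% | 81.2% | 0.2 | 4.9% | 0.5% |
| 0.02 | 81.8% | 81.3% | 0.5 | 4.8% | 1.0% |
| 0.05 | 82.9% | 81.7% | 1.3 | 4.4% | 2.6% |
| 0.10 | 84.9% | 82.3% | 2.6 | 3.9% | 5.4% |

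Losses are taken before rounding.

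**Step 3: is the R² range plausible?** A binary factor with prevalence p and a difference of δ SD explains p(1 − p)δ²/[1 + p(1 − p)δ²].
- Sex, p = 0.075, assumed δ = 0.3: 0.00624/1.00624 = 0.6%. At δ = 0.5: 1.7%.
- AUD, assumed p = 0.3 to 0.5, δ = 0.3: 1.9% to 2.2%. At δ = 0.5: 5.0% to 5.9%.

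With so few women, most of any gain comes from AUD. These shares apply to R² only if δ is read as the difference remaining after baseline drinking.

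**Step 4: simulation.** 450 participants randomised in blocks of 10 within the four sex-by-AUD cells; 7.5% women; 40% AUD (assumed), correlated with baseline drinking; 20% random dropout. Eight settings (R² of 0.01, 0.03, 0.05 and 0.10, each with d = 0 and d = 0.30) × 6,000 = 48,000 trials.
- Trials in which sex or AUD differed between arms at p < 0.05: none.
- Bias with the strata omitted: within 0.002.
- Rejection rate under no effect with the strata omitted: 4.2% to 4.8%.
- Power omitted against included: 81.2% and 82.8% at R² = 0.05; 82.1% and 84.9% at R² = 0.10.

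**Step 5: chance selection of other variables.** If k independent baseline variables are tested at 0.05 (k and the threshold are assumed), the chance that at least one is selected is 1 − 0.95^k: 40% for k = 10 and 64% for k = 20. With an assumed pairwise correlation of 0.3 it is 35% and 54%. These figures show how open the covariate set is. They do not measure harm to the estimate.

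**Step 6: provider clustering.** As an illustration, assume an intraclass correlation of 0.01 and three providers per arm. The variance of an arm mean is 0.99/180 + 0.01/3 = 0.00883. R² = 0.05 removes 0.05/180 = 0.00028, about 3% of it instead of 5%.

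**The case against.** The strongest objection is size. With no bias, no inflated error rate and about a point of power at stake, no conclusion of the trial is likely to turn on this. That is correct, and the point is offered as a modest improvement.

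The R² range may also be generous. AUD is defined by an AUDIT cut-off and the AUDIT contains consumption items, so the baseline TLFB value already in the model should absorb part of it. This stands as a caution: at R² = 0.01 the loss is only 0.2 points.

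The list of terms need not be exhaustive, and the Missing data section has another route by which baseline predictors of attrition enter the model. Sex or AUD could come in that way. This is true, but that route also depends on the data and prespecifies neither factor. The significance rule is also confined to variables thought to be related to outcome, so prognosis does filter the pool. Within that pool, however, chance imbalance still decides.

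Finally, the calculations use a single linear outcome. They do not fit the full mixed model with its provider effect, nor the count models likely for Aim 2. The figures should therefore be read as applying to Aim 1 with a linear model. For Aim 2 the gap in specification is the same, but its effect has not been quantified.

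**Conclusion.** The concern holds. Neither the Aim 1 nor the Aim 2 model names the stratification factors, and the rule for adding covariates is almost unable to select them. For a linear Aim 1 analysis with 360 participants and d = 0.30, the cost is 0.5 to 1.3 points of power, a standard error overstated by 1.0% to 2.6%, and a true test size of 4.8% to 4.4%. These figures rest on an assumed R² of 0.02 to 0.05 beyond baseline drinking; an optimistic 0.10 gives 2.6 points, 5.4% and 3.9%. The planned power is still met and the treatment estimate is not biased. The covariate set of the primary model also remains undetermined until the baseline data have been tested, which is a gap in prespecification whatever the value of R².

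**What to change.** - Name sex and AUD stratum, as randomised, as fixed covariates in the Aim 1 and Aim 2 models beside the baseline value of the outcome.
- Remove the adjustment triggered by significant baseline differences. If further baseline covariates are wanted, list them in advance for their expected relation to drinking (Aim 1) or to the Aim 2 outcome concerned.
- Report baseline balance descriptively, without tests.

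The same sentence in General analytic approach also provides for adjustment for other addictions treatment received. That is a separate question and is not covered here. The attrition route in the Missing data section is likewise left as it is, so the plan should state how it relates to the prespecified covariate set.

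The cost is analysis-plan wording only. Both factors are known at randomisation, so no new data are needed, and in the simple two-arm comparison they use 2 of 358 degrees of freedom.
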